BioVin® is much lower than reported side effects, we predict that there will be no adverse effects due to BioVin®. In addition, BioVin® is a full-spectrum grape extract and not just a concentrate of grape seed. Side effects and/or adverse events are not anticipated or expected, but the study coordinator will closely monitor for this possibility.

Green Tea Extract Adverse Events:

According to the NIH, more than five cups per day of green tea is considered “possibly unsafe” due to the side effects of the caffeine (23). These side effects can range from mild to serious and include headache, nervousness, sleep problems, vomiting, diarrhea, irritability, irregular heartbeat, tremor, heartburn, dizziness, ringing in the ears, convulsions, and confusion. In addition green tea seems to reduce the absorption of iron from food (23).

In clinical trials administering caffeinated green tea extracts, cancer patients who had an intake of 6 grams/day, in 3-6 divided doses, experienced mild to moderate gastrointestinal side effects, including nausea, vomiting, abdominal pain, and diarrhea (24,25). Some reported possible central nervous system symptoms, included agitation, restlessness, insomnia, tremors, dizziness, and confusion. These side effects were considered to be due to the caffeine in the green tea extract (25). In a four-week clinical trial that assessed the safety of decaffeinated green tea extracts (800 mg/day of EGCG) in healthy individuals, a few of the participants reported mild nausea, stomach upset, dizziness, or muscle pain (26).

Recently, oral use of green tea extracts (GTEs) has been associated with several instances of hepatotoxicity (27-30). Most affected patients were women, and many were consuming GTEs for the purpose of weight loss. Although hepatotoxicity in most cases resolved within four months of stopping GTE, there have been cases of positive rechallenge and liver failure requiring liver transplantation. A recent case report describes a case of acute liver failure requiring transplant in a woman consuming Green LiteJ capsules distributed by Origin Biomedicinals, Inc., Halifax, Canada (31). Since no other cause could be identified, the treating physicians concluded that the cause of the fulminant liver failure experienced by this subject was most likely related to the consumption of the over-the-counter GTE supplements for weight loss.

Potential Risks:

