The amount of green tea extract within NutraStem® has been calculated to be equivalent to 3-4 cups which is less than the amount reported that caused adverse effects according to NIH (23). Most important, however, the percentage of caffeine in NutraStem's green tea extract is considered quite low at a range of 32 – 42 mg per dose. The average green tea on the market has 3.12 mg of caffeine per fluid ounce or 24.96 mg per cup (8 oz.) (32, 33). Thus, the amount of caffeine in NutraStem's green tea extract is less than the amount found in 2 cups of market-grade green tea. Therefore, we do not expect to have adverse effects within this study due to the presence of green tea extract with such low caffeine content. Side effects and/or adverse events are not anticipated or expected, but the study coordinator will closely monitor for this possibility.

Wild Blueberry Extract (Lowbush Powder, VitaBlue®) Adverse Events:

Anecdotal evidence suggests that Blueberry can occasionally induce symptoms of food allergy in sensitized individuals; however, no studies have been reported to date. The lack of reported evidence may be due to the low allergenicity of this berry, the small amounts consumed, or the restricted time frame of consumption. Oftentimes a limited or low exposure to certain allergens might be the reason for the limited complaints reported. However, as the promotion of blueberry consumption continues, this situation may change (34). Nonetheless, based on adverse effects reported to other berries, and particularly to members of the same family, it can be said that blueberries may induce symptoms of food allergy in sensitized individuals (35).

For example, a 25-year-old woman reported adverse reactions due to lingonberry (*V. vitis-idaea*). While eating lingonberry jam, she developed allergic symptoms including itching wheals around her mouth, however, the symptoms dissipated. During a second episode, when she ingested a very small amount of lingonberry jam several days later, she immediately noticed more-intense symptoms, including severe itching on the mouth, tongue and throat, and wheals over the mouth. Symptoms dissipated within an hour, however, it was noted that upon secondary exposure the symptoms were more severe and a skin reactivity test demonstrated a positive allergic response to lingonberry (36).

Potential Risks:

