All quantifiable results will be expressed as mean \pm sem and will be analyzed using repeated measures Analysis of Variance (ANOVA). All post-hoc tests will be conducted using a Scheffè test. Only de-identified data will be sent to the sponsor for completion of data analysis. Subject data will be maintained by the study coordinator in a locked cabinet in CBH 508. Electronic databases will be maintained on a password protected computer. The study coordinator will create and maintain a password protected Excel master list that will contain study participants names, demographic information, study ID, and information recorded during the study sessions. Flow Cytometry results will be submitted to the research coordinator and forwarded from her to the sponsor. Data forwarded to the sponsor will be de-identified.

F. Human Subjects

Up to 60 men and women, generally healthy, age 50 to 70 with no debilitating (defined as having a chronic disease or condition that has severely limited activities of daily living, normal function, or ability to live an active life or injury). The study coordinator will explain the purpose of the study and describe all visit activities to potential participants. If they are still interested in the study they will be asked questions about their health to determine whether they are able to safely participate in the study. The “screening script” is a written tool based on the inclusion & exclusion criteria that will be used to screen all potential participants.

Inclusion Criteria

- Men or women who are 50 to 70 years of age, inclusive, at the baseline visit.
- Ability to do 15 minutes of treadmill walking exercise.
- Generally healthy

Exclusion Criteria

Subjects who meet any of the following exclusion criteria are not eligible for participation in this clinical research:

- Men and women less than age 50 or more than age 70
- Self reported history of difficult veins/difficulty obtaining blood samples
- Participated in more than 2 sessions per week of strenuous exercise in the last month
 - Are unwilling to follow the procedures of the trial, such as making visits or taking the supplements when asked to;
 - Are unable to tolerate the ingredients in NutraStem® or placebo, or who self report food allergies

- Have unintentionally lost or gained 10 or more pounds of body weight in the last 3 months;
- Have an acute illness (such as a severe cold or flu) or have been hospitalized within the past month.

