- Have severe co-morbid disease including cardiac, pulmonary, renal, hepatic, carotid, peripheral vascular disease, stroke, neurological, clotting disorders or active cancer (*defined as any condition that would cause severe limitations or inability to carry out usual activities of daily living*);
 - Have used any prescription or non-prescription products for antioxidant regimen or stem cell supplement in the 2 weeks prior to beginning this study (Alpha Tocepheral, Vitamin E, Ascorbic Acid, CoQ10)
 - Are diabetic (as defined by diagnosis, use insulin, or a fasting blood glucose value of greater than 120 mg/dl);
 - Have uncontrolled hypertension as evidenced by one of the following;
 - Systolic blood pressure (SBP) > 180 mm Hg or diastolic blood pressure (DBP) > 100 mm Hg, upon two of three repeated measures, if not on medications for hypertension.
 - Systolic blood pressure (SBP) > 150 mm Hg or diastolic blood pressure (DBP) > 90 mm Hg, upon two of three repeated measures, if on medications for hypertension;
 - Have had a recent cardiovascular event (past 36 months), or a family history of sudden death or heart attacks before the age of 55;
 - Have a Body Mass Index (BMI) of less than 20 or greater than 35 m/kg²;
 - Have participated in a clinical trial in the past 4 weeks;
 - Take methadone, insulin, anticoagulants (blood thinners), MAO's or similar medications;
 - The anticipated need for surgery of any type during the entire study;
 - Subjects who plan to donate blood or blood products during the study or for thirty (30) days following the study;
 - Subjects with evidence of active peptic ulcer disease (vomiting of blood, dark blood in stools or stools that are black or tarry, nausea or vomiting, unexplained weight loss, unexplained appetite changes, abdominal pain) or who have a reliable history of gastrointestinal bleeding within the past five (5) years;
 - Subjects with recurrent or a history of intestinal disorders that may interfere with the absorption of the product (Malabsorption Syndrome, Crohns, IBS, Ulcerative Cloitis, gastric bypass).
 - Have any disease or condition that in the investigator's opinion compromises the integrity of the clinical trial or the safety of the subject;

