The nutritional supplements being used in this research are commonly available nutritional supplements and are being used in small doses which represents minimal risk to participants. Screening for exclusion criteria will reduce this risk even further. There is no direct benefit to participants.

Blood draws may cause minor pain from the needle insertion, blood clot, or in rare cases, a bruise or infection. These risks will be minimized by the use of standard blood draw precautions.

The exercise intervention will be closely monitored for any participant discomfort by the study coordinator who is a registered nurse. The intervention will be stopped at the request of the participant, & for any reported chest pain, difficulty breathing, blood pressure increased above 180/94, or if the study coordinator believes it is in the best interests of the health of the participant. Blood pressure will be monitored during the rest and recovery phase until it has returned to baseline. If elevated blood pressure, breathing, and/or chest pain do not resolve with 15 minutes of rest or become more severe during that time EMS will be activated by the study coordinator.

Special Precautions

All measures will be taken to protect the confidentiality of participants. All individual data will be coded with a numerical code and will be kept in a locked file cabinet in the

study coordinators office (CBH 508). No other identifying information will appear on the database. All reports and potential publications will report collective information only – participants will not be identified.

Risk/Benefit Assessment

The ingestion of the nutritional supplements involved in this research poses no serious risks to healthy participants. Potential participants will be carefully screened for any medical conditions or medication use that could be impacted by the intake of these supplements. The Modified Bruce protocol was developed for people with poor cardiovascular fitness and our participants will be generally healthy. With the precautions taken to protect participant confidentiality (as mentioned above), the potential benefits of the knowledge expected to be gained from the study outweigh any potential risks.

H. Payment/Compensation

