(Exclude if severe co-morbid disease including cardiac, pulmonary, renal, hepatic, carotid, peripheral vascular disease, stroke, neurological, clotting disorders or active cancer (*defined as any condition that would cause severe limitations or inability to carry out usual activities of daily living*))

Antioxidant regimen or stem cell supplement in the 2 weeks prior to beginning this study:

_____ (exclude if took Alpha Tocepheral, Vitamin E, Ascorbic Acid, CoQ10)

Heart issues:

Self: _____ (exclude if cardiovascular event past 36 months)

Family: _____ (exclude if family hx sudden death or heart attacks before age 55)

Weight/height: _____ (exclude if BMI less than 20 or greater than 35 m/kg^2)

Other clinical trials: _____ (exclude if participated in a clinical trial in past 4 weeks)

Medications: _____
(exclude if methadone, insulin, anticoagulants, MAO's)

Any surgery planned: _____
(exclude for anticipated need for surgery of any type during study)

Blood donation: _____
(exclude if plan to donate blood or blood products during the study & for 30 days following the study)

Stomach problems: _____

(exclude if evidence of active peptic ulcer disease (vomiting of blood, dark blood in stools or stools that are black or tarry, nausea or vomiting, unexplained weight loss, unexplained appetite changes, abdominal pain))

GI bleeding: _____
(exclude if any hx GI bleed within the past 5 years)

Absorption problems: _____
exclude for:
Malabsorption Syndrome
Crohns
IBS
Ulcerative Colitis
gastric bypass

IRB APPROVED

JAN 04 2013

University of North Texas
Health Science Center

If all criteria met and still interested obtain:

NCT01847027

Mailing address: _____

Email: _____

Phone #'s: _____

Schedule for session #1 on: _____

Informed consent mailed for review: _____

Remind to fast (nothing but water after midnight) for blood draws

IRB APPROVED

JAN 04 2013

**University of North Texas
Health Science Center**

Subject ID: _____

Date: ____ / ____ / ____

NCT01847027

Demographic Form

This questionnaire asks you general demographic questions. We greatly appreciate your help.

1. Your birth-date is: _____, 19_____, making you: _____ years old

IRB APPROVED

2. Please select your ethnic origin:

Asian/Pacific Islander Native American Black

JAN 04 2013

White Hispanic Other, specify: _____

University of North Texas
Health Science Center

Your ethnicity:

Not Hispanic or Latino Hispanic or Latino

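### Green tea extract: the protocol reports liver failure, its risk text does not answer it, and the only exclusion naming the liver requires severe limitation of daily living

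*Combined protocol and SAP*

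**What the plan says.** **Hazard.** Section E, Green Tea Extract, Adverse Events: "Recently, oral use of green tea extracts (GTEs) has been associated with several instances of hepatotoxicity (27-30" (the figures are the plan's reference numbers). It adds that most affected patients were women, that many took extracts to lose weight, and that most cases resolved within four months of stopping. Some recurred on rechallenge and some came to transplantation. The same text cites a four-week safety trial of decaffeinated extract (800 mg/day EGCG) in healthy people, in which a few had mild complaints.

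**Reply.** The Potential Risks text puts the extract at 3–4 cups of tea, below the NIH level of more than five, and its caffeine at 32–42 mg per dose. It concludes: "we do not expect to have adverse effects within this study due to the presence of green tea extract with such low caffeine content". A general sentence says the coordinator will watch for side effects.

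**Exclusions.** Section F excludes severe co-morbid disease, hepatic included, "defined as any condition that would cause severe limitations or inability to carry out usual activities of daily living". The screening script repeats this under chronic illness: "Exclude if severe co-morbid disease including cardiac, pulmonary, renal, hepatic, carotid, peripheral vascular disease", with the same definition. The general provisions are an inclusion criterion of being generally healthy and an exclusion for any condition that the investigator thinks "compromises the integrity of the clinical trial or the safety of the subject". Section G says participants will be "carefully screened for any medical conditions or medication use that could be impacted by the intake of these supplements" and that taking the supplements "poses no serious risks to healthy participants".

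**Tests.** Under Blood Analysis, a 5 ml SST tube goes to an outside laboratory at each session for lipids only. The other tests are flow cytometry, four inflammation markers and a finger-stick glucose at visit 1. No liver value is taken.

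**The concern.** The reply answers a different hazard from the most serious one reported. Caffeine explains agitation or palpitations; the plan does not offer it as the cause of the liver injury. For two other ingredients the plan does engage with the specific matter: it rebuts the blood-pressure signal for the grape extract, and it reports liver findings for carnosine.

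The exclusion also measures the wrong thing. It tests how far disease limits daily activity, not whether liver disease is present. A person with diagnosed liver disease who lives normally passes the only criterion that names the liver.

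During the trial, detection depends on the participant noticing a side effect and linking it to the supplement. A symptomless injury would not surface, and a second two-week supply is handed out at visit 2.

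At stake are the protection of individual participants and the accuracy of the risk statement. The efficacy analysis is not involved.

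**Working it through.** **1. The plan's caffeine figures (Section E, Green Tea Extract, Potential Risks).** 3.12 mg per fl oz × 8 = 24.96 mg per cup, as stated. Two cups = 49.92 mg, above 42 mg, so the claim of less than two cups reproduces. The range is 32/24.96 = 1.28 to 42/24.96 = 1.68 cups. If a dose meant one capsule, two a day would give 64–84 mg, or 2.56–3.37 cups: no longer under two, but still below five cups (5 × 24.96 = 124.8 mg). On either reading the result concerns caffeine only.

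**2. The cup equivalent.** Three to four cups of market tea would carry 74.88–99.84 mg of caffeine, against the stated 32–42 mg. On the two-capsule reading, the 3–4 cups must therefore be an amount of extract, not the same caffeine conversion. Its comparator, however, is the NIH level, which the Adverse Events text attributes to caffeine side effects. Neither comparison bears on the liver.

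**3. Dose context.** The blend is 900 mg/day and green tea extract is one of several ingredients, so the extract is below 900 mg/day. Against the 6 g/day in the cited cancer trials this is below 900/6,000 = 15%. The closer comparison is the four-week trial at 800 mg/day EGCG, which matches this trial in duration and in using healthy people. Both are reassuring. But the plan gives no liver result from any of these trials, no dose for the liver cases, and no EGCG or extract amount for the product.

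**4. Who passes screening.** Take a person with diagnosed liver disease and normal daily function.
- Severe co-morbid exclusion (Section F and script): not met.
- Generally healthy: undefined, so it may or may not exclude. The text beside it in Section F uses a similar functional test for debilitating illness ("defined as having a chronic disease or condition that has severely limited activities of daily living").
- Investigator opinion: may exclude, but sets no liver rule.
- Script item on chronic illness: may bring the disease to light, but directs exclusion only if severe.

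No explicit rule reaches this person, despite the screening promise in Section G.

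**5. Number affected.** The documents give no prevalence. Assume 1–5% of people who pass the other screens: 60 × 0.01 = 0.6 to 60 × 0.05 = 3.0 enrolled, and 30 × 0.01 = 0.3 to 30 × 0.05 = 1.5 on product. These are counts of people, not of injuries.

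**6. An optional liver panel.** 60 participants × 3 visits = 180 panels. Three tests at three visits give 9 results per person. Expected healthy people flagged out of 60, from fully correlated results (60p) to independent results (60[1 − (1 − p)^9]):

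| Assumed chance above limit, per test | Fully correlated | Independent |
|---|---|---|
| p = 0.025 (upper reference bound) | 1.5 | 60 × (1 − 0.975^9) = 12.2 |
| p = 0.001 (limit well above it) | 0.06 | 60 × (1 − 0.999^9) = 0.54 |

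About half would be on placebo. A limit at the reference bound would be a nuisance; one well above it would rarely misfire. The panel would not estimate a rate: zero events in 30 leaves a one-sided 95% upper bound of 1 − 0.05^(1/30) = 9.5%.

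**The case against.** The strongest case against the point has five parts.

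- **No named risk group.** The liver-injury text does not say that existing liver disease raises the risk. It mentions women and weight-loss use, and in the transplant case no other cause was found. A reader might infer that people with milder liver disease are known to be at higher risk here; the documents do not support that. This stands, and it makes the exclusion a precaution.
- **General provisions exist.** General health, investigator opinion and the open chronic-illness question could each keep such a person out. Section F also says the criteria drew on the medical director and on ingredient research, so the threshold may be deliberate. The daily-living wording beside the health criterion qualifies debilitating illness, so it is weak evidence for reading that criterion narrowly. This also stands: milder disease is left to discretion, not knowingly admitted.
- **Reassuring evidence.** The 800 mg/day EGCG trial is the best of it, and the plan describes the individual ingredients as well established as safe. This lowers concern but does not settle it, for the reasons in step 3 of the working.
- **Disclosure.** A reader might infer that the IRB or participants were not told of the liver hazard. That cannot be concluded: the protocol reports the transplant case just above the risk text, and the consent form is a separate document not seen here.
- **Selective comparison.** Other ingredients also get generic replies; kidney stones with vitamin D and calcium are answered only by an upper intake limit. This is fair, so the contrast in the concern is illustrative only.

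The panel is a reviewer's preference. The documents give no time to onset, and the visit 1 result would come after dispensing.

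**Conclusion.** The point holds as an inexpensive safety improvement that should be made. The plan names a severe liver hazard, the reply beneath it does not address the liver, and the one criterion naming the liver turns on daily function. Known milder disease is left to discretion, which falls short of the Section G promise.

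The size is 0.6–3.0 people per 60 under the assumed 1–5% prevalence. The documents give no rate of liver injury or of milder liver disease, so the benefit cannot be quantified. A reader might take the finding to mean that the supplement is unsafe at this dose, or that liver testing is indispensable. The documents support neither. The stem-cell comparison is unaffected.

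Confidence is medium. The textual facts are plain, but the value of acting on them rests on precaution.

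**What to change.** 1. **Exclusion.** In Section F and the screening script, exclude any known liver disease by diagnosis, without the daily-living qualifier. Cost: a protocol amendment and a few extra screening exclusions (0.6–3.0 per 60 under the assumption above).
2. **Risk text.** Revise the green tea Potential Risks text and Section G to address hepatotoxicity directly, weigh the four-week EGCG trial, and state the daily extract or EGCG amount if it can be disclosed. Cost: drafting, in the same amendment.
3. **Optional panel.** Run ALT, AST and bilirubin on the existing SST tube at all three visits, so that weeks 3–4 are also covered. The investigator and medical director fix a numeric limit in advance, well above the reference bound; three times the upper bound is one proposal, not a figure from the documents.
   - A result above the limit leads to a call to stop, no further supply, and referral. At visit 3, when the four weeks are over, it leads to referral only.
   - The participant stays in follow-up and is analysed in the assigned arm. State that withheld supply is not failure to complete visit activities, so that the withdrawal rule in Section E does not apply. No unblinding is needed.
   - The visit 1 result does not gate entry.
   - Cost: fees for up to 180 panels, investigator time, occasional false alarms (including on placebo), and some participants analysed with reduced exposure. There is no extra draw or visit.
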